Unblinded M.D. investigators, who will not be involved in data collection or managing the case, will be in charge of preparing the study drugs. After consent is obtained, the recruiter will give said unblinded investigator the subject's name, subject number, weight (in kg), height (in inches), and a sealed envelope containing the subject's group assignment and instructions for drawing up the study drugs. From this information, the unblinded investigator will prepare the study medications. Both ketamine and methadone are within the standard of care and are routinely used in anesthetic care at our institution. These medications are available in all CSMC post-anesthetic care units (PACU) as multi-dose vials, and are stored in a locked cabinet only accessible to PACU nurses not involved in the study. These nurses will give the required amount of study drugs requested by the unblinded investigator. The M.D. investigator will record the amounts given to each subject on a private record sheet that is only accessible to said investigator. There will be three syringes: one for ketamine, methadone and a syringe for IV infusion. The sham fluid will be 0.9% normal saline. Dosing will be based on mg/kg for IV bolus and mg/kg/h for IV infusion. An equal volume of the sham will be given. Anesthesiologist, patient and the investigator collecting the data will not be aware of the contents of the study syringe (double blind design). Each syringe will be labeled by increasing numbers following the sequence of

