administration i.e., syringe #1 will be given pre-induction, syringe #2 will be given during induction, and syringe #3 will be infused over the duration of the surgery. To prevent accidental administration of 3 placebos, all syringes will have an additional random 4 letter label: those containing any vowel (A, E, I, O, U) at the end of the 4 letter combination will be designated as placebo syringes. The unblinded investigator will double check that no more than 2 syringes have this letter combination prior to handing off the syringes to the anesthesiologist. Once this has been verified, he will place a sticker over the alphabetic code to further blind the recruiter in case the placebo blinding procedure has been discovered. In the extremely rare event that the patient accidentally receives 3 placebos (no study drug), there is a rescue medication algorithm that calls for administering IV fentanyl boluses or increasing anesthetic depth to control pain. Date, IRB number, and subject number will be the only other labeling allowed on these syringes. Only the aforementioned unblinded M.D. investigators will know the syringe identities. However, the anesthesiologist can always be unblinded for emergencies that require identification of the study drug to direct appropriate treatment e.g., undocumented allergic reaction to the study medication, unexplained hemodynamic instability, unexplained altered mental status, etc. The unblinded investigator will meet with the anesthesiologist after the case is finished to report the amount of study drug given for pharmacy and billing purposes. The data collector, recruiter, surgeon, and nurses involved with the subject's care will not be allowed to review the anesthetic record unless given permission by the P.I. Only after the subject's completion of the study shall they have access.

Group	Study Medication (note - dose based on ideal body weight (IBW) in kg)
Ketamine	Preinduction: Sham methadone (0.9% normal saline IV bolus, volume (mL) equal to calculated methadone dose of 0.2 mg/kg) Induction: ketamine 0.5 mg/kg IV bolus Infusion: ketamine 5 mcg/kg/min IV
Methadone	Preinduction: 0.2 mg/kg methadone IV bolus Induction: Sham ketamine (0.9% normal saline IV bolus, volume (mL) equal to calculated ketamine induction dose of 0.5 mg/kg) Infusion: Sham ketamine (0.9% normal saline IV, rate equal ketamine infusion rate of 5 mcg/kg/min)

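### The only described check of the prepared syringes counts placebo codes and never compares the set with the assigned arm

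*Combined protocol and SAP*

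**What the plan says.** All of this stands in METHODS II, Study Medication Administration Protocol.

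- **Preparation.** An unblinded physician investigator prepares the study drugs from a sealed envelope that holds the group assignment and the drawing-up instructions. "There will be three syringes: one for ketamine, methadone and a syringe for IV infusion". Their order of use is fixed: "syringe #1 will be given pre-induction, syringe #2 will be given during induction, and syringe #3 will be infused over the duration of the surgery".
- **Purpose of the code.** "To prevent accidental administration of 3 placebos, all syringes will have an additional random 4 letter label".
- **Key.** The rule is that "those containing any vowel (A, E, I, O, U) at the end of the 4 letter combination will be designated as placebo syringes".
- **Check.** The same investigator is to "double check that no more than 2 syringes have this letter combination prior to handing off the syringes". The limit is the same for every arm.
- **After the check.** "he will place a sticker over the alphabetic code to further blind the recruiter in case the placebo blinding procedure has been discovered". Nothing says that the code is removed.

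The group table in that section and the dosing table in METHODS IV.e give each arm one correct pattern. The ketamine arm has saline in syringe 1 only, the methadone arm has saline in syringes 2 and 3, and the combination arm has no saline.

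**The concern.** The protocol treats a preparation error as possible, since it builds a labelling step to catch one. But the step tests for a single wrong outcome, three placebos, and the test does not use the subject's assignment. No other step is described in which the finished set is compared with the envelope, and no second person verifies it. A subject randomized to the combination could therefore be given the methadone-only set, or the reverse, and the check would raise no alarm. Such errors mix the treatments being compared, and in an analysis by assigned arm they pull the arms toward each other.

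The second, smaller issue is concealment. One rule decodes every subject's syringes, and the code goes into the operating room under a sticker. The person handling the syringes is the anesthesiologist, who is meant to be blind and who adjusts anesthetics and fentanyl during the case.

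**Working it through.** **Inputs.** Three syringes per subject, each placebo (P) or active (A), written in the order 1-2-3. The correct patterns from the medication tables are ketamine PAA, methadone APP and combination AAA. The check passes a set if it has at most 2 P. Labels are taken to match contents.

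**Step 1: the plan's own limit.** The placebo counts by arm are 1, 2 and 0, and the maximum is 2. The stated limit of 2 is thus the smallest common limit that lets every correct set through.

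**Step 2: all patterns.** There are 2 × 2 × 2 = 8.

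| Pattern | Placebos | Check | Correct for |
|---|---|---|---|
| AAA | 0 | pass | combination |
| PAA | 1 | pass | ketamine |
| APA | 1 | pass | no arm |
| AAP | 1 | pass | no arm |
| APP | 2 | pass | methadone |
| PAP | 2 | pass | no arm |
| PPA | 2 | pass | no arm |
| PPP | 3 | stopped | no arm |

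**Step 3: what gets through.**

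- *A complete set made for another arm.* Each arm has 2 such sets and both pass: 2 of 2 per arm, 6 of 6 overall.
- *Any wrong pattern.* Each arm has 8 − 1 = 7 wrong patterns. Only PPP is stopped, so 6 of 7 pass (18 of 21 over the three arms).
- *One syringe wrong.* There are 3 arms × 3 syringes = 9 such errors, and 8 pass. The one caught is a methadone-arm set whose syringe 1 became placebo (APP to PPP).

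**Step 4: the same count under two alternative rules.**

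- *Require the arm's own number of placebos (1, 2 or 0).* The wrong patterns that still pass are APA and AAP for ketamine, and PAP and PPA for methadone: 4 of 21.
- *Require the arm's own pattern, syringe by syringe.* By construction 0 of 21 pass.

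**Step 5: what the code reveals.** In a correctly prepared set the number of final vowels (1, 2 or 0) is different in each arm. A vowel on syringe 1 means ketamine, and a vowel on syringe 2 or 3 means methadone. A consonant on one syringe leaves two arms possible, and reading syringes 1 and 2 together always settles it.

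**The case against.** **The check does what it claims.** It is presented only as a guard against three placebos, and if the labels are right it works. Getting the right drugs into the right set rests on the envelope and its instructions. Nurses outside the study release the requested amounts, the preparer records what was given, and the amount given is reported after the case, so a ketamine/methadone mix-up might be traced later. This stands, and it limits the point. But none of these steps is described as a comparison of the finished set with the assignment before use.

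**The counts are not risks.** This also stands. A reader might infer that 86% (6/7) is the chance that a preparation error goes unnoticed, or the share of wrong-arm sets that pass. It is neither. It weights all patterns equally, and 5 of the 7 wrong patterns per arm belong to no arm. The figure for sets belonging to another arm is 2 of 2.

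**No effect on the result is shown.** A reader might also infer a definite dilution of the opioid contrast. If a share *e* of sets in one of two compared arms held the other arm's drugs, a difference *d* would become *d*(1 − *e*); with share *e* in both arms it would become *d*(1 − 2*e*). For the planned 18.9, *e* = 1% gives 18.7 or 18.5, and *e* = 5% gives 18.0 or 17.0. Both rates are assumptions, and the documents supply none. The power reading also depends on the base. With 38 per group and SD 23, *e* = 5% takes power from 94% to 92% or 89% if the true difference is 18.9, and from 80% to 76% or 71% if it is 15. The documents do not support choosing any of these as the consequence.

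**The blind is not shown to be broken.** Someone must lift a sticker to read a code. The unblinded investigator reports the amount of study drug to the anesthesiologist once the case is over, PACU orders come from a standardized set (METHODS VI), and later pain control passes to the surgical team or pain service (METHODS VII). The surgeon, nurses, recruiter and data collector have no access to the anesthetic record until the subject has finished, unless the principal investigator permits it. What remains is a mainly intraoperative exposure, and the sticker is described as protecting the recruiter although the syringes go to the anesthesiologist.

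**Conclusion.** The point holds as a weakness in procedure. The one described check of the prepared set is blind to the assigned arm. It passes every complete set made for another arm and 6 of the 7 wrong patterns for any arm. This follows from the protocol's own tables and pass rule, on the assumption that labels match contents. It does not show that errors will happen, how often, or that power or the treatment contrast would suffer.

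The fixed vowel key under a sticker is a secondary, smaller point: a lifted sticker can reveal the arm during the case. Severity is minor. The reason to act is that a strictly better check is available at the same step for almost nothing.

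**What to change.** In METHODS II, replace the limit of two placebo-coded syringes with a match to the assignment, for example: *Before hand-off, the unblinded investigator compares syringes 1, 2 and 3 with the pattern for the group named in the envelope (ketamine: placebo in 1 only; methadone: placebo in 2 and 3; combination: none) and releases the set only if all three agree.* This also excludes three placebos, so the existing purpose is kept.

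Then remove the letter code after the check and before hand-off, instead of covering it.

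**Cost.** A few seconds per case, by the same person at the same step. The dosing tables do not change.

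**Limit.** The match reads labels. It would not detect a syringe whose label does not match its contents. Because the code separates only placebo from active, it would also not detect one active drug drawn up in place of the other.

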	2	If persist: phenylephrine 100 mcg (max. 300 mcg)		If persist: labetalol 5 mg (max. 15 mg)
	3	If persist: reduce infusion of study drug by 50%		If needed, hydralazine 5 mg (max. 20 mg)
Tachycardia > 100 bpm	1	Desflurane decrease by 50% to a min. of 2%	Desflurane increase by 50% to a max. of 8%	Desflurane increase by 50% to a max. of 8%
	2	If persists: phenylephrine 100 mcg (max 300 mcg)	If persists: labetalol 5 mg (max 15 mg)	If persists: labetalol 5 mg (max. 15 mg)
	3	If persists: reduce infusion of study drug by 50%	If persists: give fentanyl 50 mcg boluses	If persists: give fentanyl 50 mcg boluses

Minimum mean arterial blood pressure = 55 mmHg

VI. Surgery Conclusion

Anesthetic and study drug infusion will be discontinued at skin closure. Patients will be extubated in the operating room and transferred to the PACU. VRS pain scores will be collected immediately upon arrival. The anesthesiologist will decide which postoperative pain medications to administer, but must use a standardized computer order set in CS-link. This set gives the option of using the following opiates: hydromorphone IV, fentanyl IV, or acetaminophen-hydrocodone PO. Ondansetron 4 mg IV will be given for nausea and vomiting. VRS pain scores will be measured again prior meeting PACU discharge criteria (awake and alert with stable vital signs and the absence of intractable side effects)

VII. Postoperative Period

- a. After PACU discharge, pain control will be assumed by the primary surgical team or inpatient pain service. Pain medication regimens commonly include PRN dilaudid IV and oral narcotics e.g., percocet (oxycodone/acetaminophen) or norco (hydrocodone/acetaminophen). Thus, patients will always receive some form of narcotic as a part of their pain medication regimen.

PATIENT DATA COLLECTION

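### The routine report of study drug amounts to the blinded anesthesiologist is not tied to PACU discharge, so the plan permits an arm-aware prescriber during PACU care

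*Combined protocol and SAP*

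**What the plan says.** **Blinding.** Methods II (Study Medication Administration Protocol) states: "Anesthesiologist, patient and the investigator collecting the data will not be aware of the contents of the study syringe (double blind design". It reserves knowledge of syringe identities to the unblinded physician investigators, who keep the amounts on a private sheet.

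**Emergency exception.** The same section says that "the anesthesiologist can always be unblinded for emergencies that require identification of the study drug to direct appropriate treatment".

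**Routine disclosure.** Methods II then says, without condition, that the unblinded investigator "will meet with the anesthesiologist after the case is finished to report the amount of study drug given". The stated purpose is pharmacy and billing.

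**Record access.** The data collector, recruiter, surgeon and nurses "will not be allowed to review the anesthetic record unless given permission by the P.I"; otherwise they gain access only once the subject has completed the study. The anesthesiologist is not on that list.

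**PACU prescribing.** Methods VI (Surgery Conclusion): "The anesthesiologist will decide which postoperative pain medications to administer, but must use a standardized computer order set in CS-link". On the content of the set: "This set gives the option of using the following opiates: hydromorphone IV, fentanyl IV, or acetaminophen-hydrocodone PO".

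**Handover.** Methods VII (Postoperative Period): "After PACU discharge, pain control will be assumed by the primary surgical team or inpatient pain service".

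**Outcomes.** For the PACU, Methods VI says "VRS pain scores will be collected immediately upon arrival" and adds a second score before discharge criteria are met. Patient Data Collection IV records PACU opioid requirements, and total opioid consumption at 24, 48 and 72 hours after surgery.

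**The concern.** Emergency unblinding is an ordinary safeguard. The billing meeting is different: it happens for every subject, serves an administrative purpose, and goes to the person who chooses analgesia in the first hours after surgery. If it takes place while the patient is in the PACU, that prescriber can order differently by arm, knowingly or not.

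At stake are outcomes the trial relies on. Opioid consumption is the secondary hypothesis (Background) and the outcome on which 38 per group was set (Data Analysis). Pain scores are the main hypothesis, and the second PACU score is taken after PACU analgesia has been given.

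**Working it through.** The question is one of timing and roles, so the main check sets the passages against each other.

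1. **Does the report reveal the arm?** Methods II says that the amount of study drug is reported. It does not say that the amount is itemised by drug. By the dosing table, the ketamine arm receives ketamine only, the methadone arm methadone only, and the combination arm both. Amounts by drug therefore identify the arm uniquely, and pharmacy and billing need amounts by drug. The plan also guards the same information elsewhere, through the private sheet and the restricted anesthetic record. The inference is strong but remains an inference.

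2. **When is it made?** After the case is finished. Neither that sentence nor any other defines the case or mentions PACU discharge, the last PACU pain score or the end of PACU prescribing.

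3. **Who prescribes, and until when?** The anesthesiologist, until PACU discharge (Methods VI and VII). Nothing gives PACU orders to another clinician, or bars an informed anesthesiologist from writing or changing them.

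4. **Which outcomes arise in that window?**
   - PACU opioid use: directly exposed.
   - The second pain score, before PACU discharge: exposed, because it follows PACU treatment.
   - The 24, 48 and 72 hour opioid totals: exposed to the extent that they include PACU doses. That is the natural reading of totals following surgery, but PACU requirements are listed separately and inclusion is not stated.
   - The arrival pain score: little exposed, because it is taken at once.

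5. **What limits the exposure?** PACU IV opioid administration is based on pain scores (Summary of Study Design). The order set is standardized. Opioids are converted to morphine equivalents, so a change of agent alone need not move the total. The patient and data collector are blinded. The PACU stay is 1-3 hours (Potential Risks).

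6. **Can the bias be sized?** No. The plan's 38 per group reproduces: difference 15 mg, SD 23 mg, effect size 15/23 = 0.652, two-sided alpha 0.05 and power 80% give 37.9 by the exact t calculation, rounded up to 38. That supplies a yardstick of 15 mg, but no document gives the amount by which an informed prescriber would change orders, or in which arms.

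   An illustration shows how much rests on that choice. Assume no true drug effect, normal data, n = 38 per arm (df = 3 × 38 − 3 = 111), an overall F test at 0.05 and then Newman-Keuls, with an invented shift of 5 mg less opioid (5/15 = 33% of the yardstick). The rate of falsely finding the combination better than both single drugs is:

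   | Assumed pattern | SD 23 | SD 38 |
   |---|---|---|
   | No shift | about 0.3% | about 0.4% |
   | Shift in both methadone-containing arms | 1.2% | 0.8% |
   | Shift in the combination arm only | about 5% | 2.0% |

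   At SD 23 the answer changes about fourfold with the pattern alone. These rates describe the assumptions, not the trial, and they are not upper limits.

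**The case against.** The strongest reply is that this is undefined timing and not a planned unblinding. The case may well be meant to include the PACU stay, and PACU orders may be entered before the meeting. A reader might infer that the plan unblinds the anesthesiologist before PACU care. The documents do not support that: they allow it without requiring it.

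A second reply is that the remaining discretion is small. Pain scores drive IV dosing, the order set restricts the choice of opioid, and no passage shows how knowledge of the arm would change the milligrams given. This stands as a limit on size. It does not remove the point, because the anesthesiologist still decides among two IV opioids and one oral combination product.

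A reader might also infer that the bias would favor the combination, or would fall mainly on its comparison with ketamine alone. Neither follows. The affected comparison depends on which arms an informed prescriber would treat differently, as step 6 shows. Less PACU opioid in an arm could also raise its second pain score, which would work against the main hypothesis.

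Finally, delaying disclosure might seem to matter for safety, since Potential Risks notes that respiratory depression risk may rise when sedatives are added after methadone. The emergency route remains open throughout, so access to the assignment when treatment requires it is unaffected.

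**Conclusion.** The point holds in a limited form. Followed as written, the plan allows a routine administrative step to tell the PACU prescriber the arm while PACU opioid use and the pre-discharge pain score are still being generated. This rests on two inferences: that the report is itemised by drug, and, for the 24 to 72 hour totals only, that they include PACU doses. The exposure lasts no longer than the 1-3 hour PACU stay and is reduced by the plan's own safeguards. The size and direction of any bias are unknown, so no error rate should be attached to it. It would be wrong to conclude that the double blind fails or that the opioid comparison is invalid. The severity is minor; the point is worth acting on because the correction is so cheap.

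**What to change.** Reconcile the blinding statement and the billing sentence in Methods II with the prescribing role in Methods VI. Amend the billing sentence so that the routine report to the anesthesiologist is made only after the subject's PACU discharge and after the pre-discharge pain score has been recorded. If the end of the case was always meant to include the PACU stay, the same clause makes that explicit. Leave the emergency unblinding route unchanged.

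The cost is one clause and a pharmacy and billing entry delayed by about the length of the PACU stay (1-3 hours). No dose, clinical rule, sample size or analysis changes.
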